4.4. Populations

The survey will be administered to HCPs and patients in the United Kingdom (UK, if product uptake does not allow for participation, another comparable EU country will be selected), Germany, and one additional EU country, to be determined based on product launch and market uptake. The timing of survey implementation will vary according to the individual country launch plans and the extent of Humalog 200 units/ml KwikPen uptake after launch. Screening questions will be used to determine respondent eligibility.

HCPs:

HCPs involved in the treatment and management of patients with diabetes who are aware of the insulin product Humalog 200 units/ml KwikPen will be eligible. The respondent population will include a mix of prescribers who have and have not prescribed Humalog 200 units/ml. Those employed in research full-time or hospital administration and those who have ever worked for or have immediate family members who have ever worked for Eli Lilly and Company (Lilly), United BioSource (UBC), or any national regulatory agency, such as but not limited to European Medicines Agency (EMA), Medicines and Healthcare products Regulatory Agency (MHRA) and Federal Institute for Drugs and Medicinal Devices (BfArM) will be excluded.

Patients:

Patients who are 18 years or older, have diabetes and have been prescribed Humalog 200 units/ml KwikPen will be eligible. Those who have ever worked for or have immediate family members who have ever worked for Lilly, UBC, or any national regulatory agency, such as but not limited to EMA, MHRA, and BfArM will be excluded.

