Eligible HCPs will receive an invitation letter via email if an email address is available, or a letter in the postal mail inviting them to participate in the survey. The invitation letter (Appendix I.2) will include: an overview of the rationale for the survey, information on how to access the survey online and by telephone, and a unique User Identification (ID) to ensure that the invitation is used only once.

HCPs in the applicable countries who are involved in the treatment and management of patients with diabetes will be invited to participate in the survey. The respondent population will include a mix of prescribers who have and have not prescribed Humalog 200 units/ml. The response rate will be monitored throughout the data collection period. Reminder notices will be sent via email and postal mail, and telephone calls will be made periodically to HCPs who have been invited

but not yet participated. The HCPs that complete the survey will be reimbursed for their time spent participating as governed by local laws and country regulations.

Patients:

Surveys targeting eligible patients will be administered via the Internet, which will allow respondents to participate at a time and location that is convenient for them, and by telephone, to allow participation of respondents who do not have Internet access or are not computer literate. Both modalities will offer the same survey.

Patients will be recruited via study packets that will be provided to HCPs due to privacy concerns in the EU. All HCPs who receive an invitation to participate in the HCP survey will also receive a study packet of patient invitations in the postal mail and a letter asking them to invite eligible patients to participate in the survey. The packet will contain 10 invitation letters to be distributed. The patient invitation letter (Appendix I.4) will include an overview of the rationale for the survey, information on how to access the survey online, the toll-free number for accessing the telephone survey, and a unique User ID to ensure that the invitation is used only once. The HCPs will not be asked to select specific patients based on eligibility criteria. HCPs will forward the patient invitations to their patients for whom they have prescribed Humalog 200 units/ml. In the event an HCP has prescribed Humalog 200 units/ml to more than 10 patients, the HCP will arbitrarily select 10 patients regardless of any additional eligibility criteria.

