9.2.1. Inclusion criteria

The HCPs must meet the following criteria to be eligible for inclusion in the survey:

- HCPs are aware of the insulin product Humalog 200 units/ml KwikPen; and
- HCPs are involved in the treatment and management of patients with diabetes.

Patients must meet all of the following criteria to be eligible for inclusion in the survey:

- Patients are 18 years or older;
- Patients have diabetes; and
- Patients have been prescribed Humalog 200 units/ml KwikPen.

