9.2.2. Exclusion criteria

The HCPs meeting any of the following criteria will not be included in the survey:

- Employed in full time research or hospital administration (i.e., non-practising physicians)
- Current or past employment by Lilly, UBC, or any national regulatory agency, such as but not limited to EMA, Medicines and MHRA and BfArM

Patients meeting any of the following criteria will not be included in the survey:

- Patients with diabetes who are not prescribed Humalog 200 units/ml KwikPen
- Current or past employment by Lilly, UBC, or any national regulatory agency, such as but not limited to EMA, MHRA, and BfArM

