This survey should take approximately 15 minutes to complete. If you cannot complete the survey at this time, please return when you can. Once you begin the survey you will need to answer all questions; you will not be able to access the survey again if you exit.

Thank you in advance for your participation. Please note the application will time out after 30 minutes of inactivity.

If you are ready to begin the survey at this time, please click continue. If not, click Return Later.

Please note: Do not use the browser's back button during this survey.

[END WELCOME PAGE]

[BEGIN SCREENING QUESTIONS]

Please provide a response to all questions and statements.

1. Do you agree to take part in this survey about Humalog[®] 200 units/ml KwikPen[™]?
 - Yes
 - No **[TERMINATE]**

2. Have you been diagnosed with diabetes?
 - Yes
 - No **[GO TO Q9; TERMINATE AFTER Q12]**
 - I don't know **[GO TO Q9; TERMINATE AFTER Q12]**

3. How long have you had diabetes?
 - Less than 1 year
 - 1 – 5 years
 - 6 – 10 years
 - 11 – 15 years
 - More than 15 years
 - I don't know
 - I don't have diabetes**[GO TO Q9; TERMINATE AFTER Q12]**

4. Do you use injectable insulin to treat your diabetes?
 - Yes
 - No **[GO TO Q6; TERMINATE AFTER Q12]**
 - I don't know **[TERMINATE AFTER Q12]**
 - I don't have diabetes **[TERMINATE AFTER Q12]**

5. For how long have you been using injectable insulin to manage your diabetes?
- Less than 1 year
 - 1 – 5 years
 - 6 – 10 years
 - 11 – 15 years
 - More than 15 years
 - I don't know
 - I don't have diabetes/I don't use insulin **[GO TO Q9; TERMINATE AFTER Q12]**
6. Have you been prescribed Humalog 200 units/ml KwikPen at least once?
- Yes
 - No **[GO TO Q8; TERMINATE AFTER Q12]**
 - I don't know **[GO TO Q8; TERMINATE AFTER Q12]**
 - I don't have diabetes/I don't use insulin **[GO TO Q8; TERMINATE AFTER Q12]**
7. For how long have you been using Humalog 200 units/ml KwikPen?
- I have not used it yet
 - Less than 3 months
 - 3 – 6 months
 - 7 – 12 months
 - More than 1 year
 - I don't know

- I don't have diabetes/I don't use Humalog 200 units/ml KwikPen **[GO TO Q9; TERMINATE AFTER Q12]**
8. What type of insulin did you use prior to using Humalog 200 units/ml KwikPen?
- Humalog 100U/ml
 - Other 100U/ml insulin
 - I don't know/I don't remember
 - I don't have diabetes/I don't use Humalog 200 units/ml KwikPen **[TERMINATE AFTER Q12]**
9. What is your gender?
- Male
 - Female
10. What is the highest level of education you have completed?

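### The patient screener does not implement the stated eligibility: patients once prescribed the 200 units/ml pen who have stopped it are kept or dropped inconsistently

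*Protocol*

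**What the plan says.** **Ever prescribed.** The patient inclusion criterion in 9.2.1 reads "Patients have been prescribed Humalog 200 units/ml KwikPen". The abstract (4.4) agrees: adults who "have diabetes and have been prescribed Humalog 200 units/ml KwikPen will be eligible". Invitations follow the same rule in 9.2: "HCPs will forward the patient invitations to their patients for whom they have prescribed Humalog 200 units/ml", and prescribers are told not to select on eligibility criteria. Question 6 of the patient survey asks "Have you been prescribed Humalog 200 units/ml KwikPen at least once". The patient screening items listed in 9.4 are agreement, diabetes diagnosis, prescription of the pen, age and employment. Current use is not among them, and time on insulin, time on the pen and previous insulin are listed there as demographic data.

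**Leaning to current use.** The exclusion criterion in 9.2.2 is in the present tense: "Patients with diabetes who are not prescribed Humalog 200 units/ml KwikPen". Section 9.9 describes the intended sample as patients under treatment with the pen.

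**The screener (Appendix I.3).** Question 4 asks "Do you use injectable insulin to treat your diabetes", and one answer is routed "No [GO TO Q6; TERMINATE AFTER Q12". In question 7, on duration of pen use, the last option combines not having diabetes with "I don't use Humalog 200 units/ml KwikPen [GO TO Q9; TERMINATE AFTER Q12". A similar combined option closes question 8. In question 7 the not-yet-used option, every duration band and the don't-know option carry no termination instruction.

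**The concern.** The screener alone decides whether an invited patient stays in, because prescribers do not filter invitations. It applies a condition that the eligibility text does not contain, and applies it unevenly.

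The patients affected belong to the question being asked. Receipt of the patient communication is anchored to the first prescription (9.1; question 15A), so it applies fully to someone who later stopped. Understanding of the key messages (question 14) applies as well, including the message about changing between strengths, since a patient who went back to the 100 units/ml product has made such a change.

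The loss cannot be repaired after data collection. Respondents cannot go back to an answered question (9.4.1), access codes are deactivated on use (9.4), and only complete surveys are analysed (10.2). Patients who meet 9.2.1 would appear in the 9.7 tables as ineligible, and their understanding and receipt would never have been recorded.

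**Working it through.** **1. Trace of the skip logic.** Each type of adult below meets 9.2.1.

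| Patient | Route | Result |
|---|---|---|
| Prescribed the pen, no longer on injectable insulin | Question 4 No; question 6 is asked but cannot reverse the termination | Dropped |
| Prescribed the pen, now on another insulin, says at question 7 that the pen is not used | Last option of question 7 | Dropped |
| Same patient, gives a past duration or don't know at question 7, then a previous insulin at question 8 | No termination instruction met | Kept |
| Prescribed the pen, not yet started, on another insulin | Not-yet-used option at question 7 continues; kept if a previous insulin is given at question 8 | Kept |
| Current user | No termination instruction met | Kept |

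Rows 2 and 3 are the same kind of patient with opposite outcomes.

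**2. Test against each population.** Under an ever-prescribed population, rows 1 and 2 are wrong. Under a current-user population, rows 3 and 4 are wrong. The screener fits neither.

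**3. The plan's own precision figures.** Equation 1 in 9.5 gives half-width = 1.96 × √[p(1 − p)/n]. At n = 280 and p = 50, 60, 70, 80 and 90%, this gives 5.86, 5.74, 5.37, 4.69 and 3.51 points. Table 1 (5.9, 5.7, 5.4, 4.7, 3.5) is reproduced.

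**4. What a bias would depend on.** Let f be the share of eligible patients whom the screener drops and d the difference in proportion correct between those kept and those dropped. The rate in all eligible patients is (1 − f) × p(kept) + f × p(dropped), so the reported rate differs from it by f × d. The documents give neither f nor d, nor the sign of d. Purely as an assumed range:

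- f = 5%, d = 10 points: 0.05 × 10 = 0.5 points
- f = 20%, d = 20 points: 0.20 × 20 = 4 points
- f = 40%, d = 30 points: 0.40 × 30 = 12 points

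The half-widths are 3.5 to 5.9 points, so the shift could be negligible or larger than the sampling error.

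**5. Precision after the change.** If 30% of 280 completers were former users (an assumption), current users number 0.70 × 280 = 196. At p = 50% the half-width is 1.96 × √(0.25/196) = 1.96 × 0.5/14 = 7.0 points, against 5.9 for all 280.

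**The case against.** A reader might infer that understanding and receipt would be measured only in patients who stayed on the pen. The text does not support that. Patients who have not started it pass question 7, and so do former users who give a past duration or don't know. Question 8 asks what was used before the pen, and a former user can answer it truthfully without being terminated. Removal is uneven, not complete.

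A reader might also infer that the results would be too favourable because patients who stopped were confused or had a dosing error. Nothing in the documents links stopping to poorer understanding or receipt.

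The combined closing options may have been meant only to catch people who do not belong in the survey. The wording of 9.2.2 and 9.9, and the endpoint about considering the messages during administration (question 15C), suit current users. The effectiveness criterion is a majority, so a shift of a few points changes a conclusion only near 50%. Section 9.7 reports ineligible patients with reasons, so the loss would be counted, and the survey is still labelled a draft.

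All of this limits what can be said about the size of the effect. It does not remove the contradiction. Section 9.2.2 speaks of prescription, not use, and a current-user intention is not carried out either. Counting the screen-outs shows how many there were but not what they understood.

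**Conclusion.** The concern holds as a contradiction within the protocol. The draft screener drops some patients who satisfy 9.2.1, keeps others in the same position, and matches neither an ever-prescribed nor a current-user population. The eligibility statements also conflict among themselves: 4.4, 9.2, 9.2.1 and question 6 on one side, 9.2.2 and 9.9 on the other.

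This conclusion rests on the text and on the skip instructions as printed, not on any bias estimate. The size and direction of bias cannot be derived, and the 0.5 to 12 points above are an illustration on assumed inputs. The point needs correcting before programming because the misclassification cannot be undone afterwards and the repair is small.

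**What to change.** State one patient population and make 4.4, 9.2.1, 9.2.2, 9.4, 9.9 and the screener agree with it.

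If ever-prescribed stands:

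- Let question 6 decide. No at question 4 continues to question 6 and terminates only if the answer there is not Yes.
- Add a non-terminating option to question 7, such as 'I used it but have stopped'.
- Reword the closing option of question 8 so that it does not catch former users.
- Restrict question 15C to patients using the pen, or ask former users in the past tense.
- Report understanding and receipt for all ever-prescribed patients, with current and former users also shown separately.

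If current users are intended, 4.4, 9.2.1 and 9.4 must say so, and questions 6 and 7 must apply that rule to former users and to patients who have not started.

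Under the ever-prescribed option the cost is one new response option, a few changes to skip instructions and wording, and one extra table split. The target of 280 need not change. The current-user subset, and the denominator of question 15C if restricted, becomes smaller and its interval wider, as in step 5 of the working.

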- HCP medical specialty (for example, endocrinology, primary care)
- Number of years practicing medicine/nursing
- Number of Humalog 200 units/ml KwikPen-treated patients the HCP managed in the 12 month period preceding the survey (self-reported)

Data pertaining to evaluation of the effectiveness of the risk minimisation measures:

The survey includes questions/statements that will assess the risk understanding and behaviour of the HCPs. The understanding level and behaviours will be analysed using descriptive statistics and CIs and will be used to determine the effectiveness of the risk minimisation measures:

- Awareness of the DHPC on the correct use of Humalog 200 units/ml KwikPen
- Understanding of the key risk messages

- Self-reported practices with respect to communication of the key risk messages in clinical practice

Patients:

Screening questions:

- Agreement to participate
- Diagnosis of diabetes
- Prescribed Humalog 200 units/ml KwikPen
- 18 years or older
- Prior or current employment by Lilly, UBC, or any national medical governing body, such as but not limited to EMA, MHRA, and BfArM

Data on demographic characteristics:

- Age
- Sex
- Country
- Education status
- Length of time with diabetes
- Length of time on any insulin therapy
- Length of time on Humalog 200 units/ml KwikPen
- Length of time on Insulin used prior to Humalog 200 units/ml

Data pertaining to evaluation of the effectiveness of the risk minimisation measures:

The survey includes questions/statements that will assess the risk understanding and behaviour of patients. The understanding level and behaviours will be analysed using descriptive statistics and CIs and will be used to determine the effectiveness of the risk minimisation measures:

- Awareness of the Important Safety Information for Humalog 200 units/ml KwikPen
- Receipt of or access to the Important Safety Information
- Understanding of the key risk messages
- Patient behaviour with respect to the key risk messages

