9.7. Data analysis

Data collected from the survey will be reported as descriptive statistics. Frequency distributions with 95% CIs will be calculated for respondent responses to all questions that address the survey objectives. Responses to each question relating to the key risk messages will be categorised as “Correct response” and “Incorrect response”. “I don’t know” is generally categorised as an incorrect response unless otherwise specified.

In addition to the overall analysis, survey data will be analysed to determine if there are any differences by country and, for HCPs, medical speciality. Sub-group analyses will include all requested subgroups including patients switched from other 100 units/ml insulins, Humalog 100 U/ml, how long patients were on insulin, and which other insulins have been used as captured in the questionnaire. Additionally, a subgroup analysis will be performed to identify possible differences in the responses based on length of Humalog 200 units/ml use.

The following will be reported as part of the analysis:

HCPs:

- *Survey administration*
 - The number of survey invitations issued by strata (i.e., by country and specialty)
 - The number of survey invitations returned due to incorrect mailing address of HCPs invited to participate in the survey
 - The number of HCPs who responded to the invitation to participate in the survey
 - The number of HCPs eligible for participation in the survey
 - The number of ineligible HCPs along with the reasons for ineligibility
 - The number of eligible HCPs who completed the survey
- *Demographic characteristics of participants*
 - Distribution of participants by age groups
 - Distribution of participants by sex
 - Distribution of participants by practice setting
 - Distribution of participants by country
 - Distribution of participants by medical specialty
 - Distribution of participants by years in medical practice
 - Distribution of participants by number of patients treated with Humalog 200 units/ml KwikPen
- *Responses to questions pertaining to the survey objectives:*
 - Awareness of the DHPC on the correct use of Humalog (insulin lispro) 200 units/ml KwikPen
 - Understanding of the risk messages
 - Self-reported practices with respect to communication of the key risk messages in clinical practice

Patients:

- *Survey administration*
 - The number of HCPs asked to invite patients to participate
 - The number of invitations provided to HCPs

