| 
B My doctor or nurse offered to explain the information in IMPORTANT SAFETY INFORMATION FOR Humalog 200 units/ml KwikPen (insulin lispro).
 |  |  |  |
| 
C I think about the important safety information for Humalog 200 units/ml KwikPen to remind myself of the risks when injecting my insulin.
 |  |  |  |

16. Other than the information you received from your doctor or nurse, from what sources have you received and/or accessed information on the safe use and understanding of the *Humalog 200 units/ml KwikPen*. Please select all that apply

Pharmacist

Other Medical Professional

Diabetes Support Group

Internet

Other

[PHONE ONLY: BEGIN SAFETY EVENT/PRODUCT COMPLAINT]

(INTERVIEWER: Please record if respondent spontaneously reported a safety event or product complaint during the course of this interview.)

- Yes
- No **[GO TO CLOSING 1a]**

Enter Safety Event or Product Complaint Verbatim

[MULTILINE INPUT]

(INTERVIEWER: Refer to Project Specific Procedure for next steps.)

[END SAFETY EVENT/PRODUCT COMPLAINT]

[CLOSING 1 DISPLAY ONLY IN [ENTER COUNTRIES OFFERING PAYMENT]]

We would like to send you [AMOUNT/TYPE] as compensation for your time and effort, but need your name and address to do so. Do you agree to provide your contact information for this purpose?

- Yes
- No **[GO TO CLOSING]**

FIRST NAME: **[FREE TEXT]**

LAST NAME: **[FREE TEXT]**

MIDDLE INITIAL: **[OPTIONAL; MUST BE 1-DIGIT ALPHA CHARACTER]**

ADDRESS: **[MULTILINE INPUT]**

CITY: **[FREE TEXT]**

COUNTRY: **[DROP-DOWN LIST INPUT WITH COUNTRIES TABLE]**

POSTAL CODE: **[FREE TEXT]**

[CLOSING 2]

This completes the survey. Thank you again for your participation.

[END SURVEY CONTENT]

**APPENDIX I.5 DIRECT HEALTHCARE PROFESSIONAL COMMUNICATION
ON THE CORRECT USE OF *HUMALOG 200 UNITS/ML KWIKPEN***

**APPENDIX I.6 PATIENT COMMUNICATION: IMPORTANT SAFETY
INFORMATION FOR HUMALOG[®] 200 UNITS/ML KWIKPEN[™] (INSULIN LISPRO)**

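### The patient screener does not match the inclusion criteria: Questions 4 and 7 can end the survey for patients the criteria admit, and Question 8 has no true answer for some of them.

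*Protocol*

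**What the plan says.** **Eligibility.** Protocol Section 9.2.1 introduces the patient criteria with "Patients must meet all of the following criteria to be eligible for inclusion in the survey" and lists three: age 18 or older, diabetes, and "Patients have been prescribed Humalog 200 units/ml KwikPen". The screening items in Section 9.4 repeat this as "Prescribed Humalog 200 units/ml KwikPen" and include no item on current use. Question 6 of the patient survey (Appendix I.3) asks about at least one prescription. The exclusion in Section 9.2.2 is in the present tense: "Patients with diabetes who are not prescribed Humalog 200 units/ml KwikPen".

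**Screener (Appendix I.3).**
- Question 4 asks "Do you use injectable insulin to treat your diabetes". A 'No' goes on to Question 6 but is flagged to end the survey after Question 12.
- Question 7 asks how long the product has been used. It offers a not-yet-used option, duration bands, 'don't know', and a do-not-use option that ends the survey.
- Question 8 asks "What type of insulin did you use prior to using Humalog 200 units/ml KwikPen". The choices are Humalog 100, another 100 U/ml insulin, don't know or remember, and a do-not-use option that ends the survey.

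**Forced response.** Section 9.9.1 requires every question presented to be answered before an Internet or telephone survey counts as complete.

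**Use of the answers.** Section 9.7 reports the distribution of prior insulin and plans subgroups for "patients switched from other 100 units/ml insulins, Humalog 100 U/ml, how long patients were on insulin, and which other insulins have been used". It also plans a subgroup analysis by length of use of the product.

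**The concern.** The written criteria and the instrument that applies them define different populations. Section 9.2 has healthcare professionals pass invitations to patients for whom they have prescribed the product, without selecting on eligibility. Patients who have stopped, or not yet started, can therefore be invited. The screener then removes some of them under conditions that Section 9.2.1 does not contain, and they would be counted as ineligible in the survey administration table.

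Question 8 is a separate problem of measurement. One of the two patient key messages in Section 8 concerns switching between strengths of Humalog. A patient who never switched, or who came from another strength, should be distinguishable from one who switched from a 100 U/ml insulin and from one who cannot remember. The printed options do not allow that.

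Neither problem can be repaired in the analysis. A terminated respondent gives no answers on understanding, and a category that was never offered cannot be reconstructed.

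**Working it through.** **1. Skip logic as printed, for respondents who meet Section 9.2.1**

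| Respondent | Q4 | Q6 | Q7 | Q8 | Outcome |
|---|---|---|---|---|---|
| Current user, earlier Humalog 100 | Yes | Yes | duration | Humalog 100 | continues |
| Stopped, other insulin now, literal answer | Yes | Yes | does not use | not reached | ended |
| Stopped, other insulin now, gives past duration | Yes | Yes | duration | Humalog 100 | continues |
| Prescribed in the past, no insulin now | No | Yes | duration | any | ended |
| Prescribed as first insulin, not yet started | No | Yes | not yet used | don't know | ended |
| Product is first insulin, in use | Yes | Yes | duration | don't know (untrue) | continues, misrecorded |
| Product is first insulin, in use | Yes | Yes | duration | does not use (untrue) | ended |

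Three things follow.
- Ending on a 'No' at Question 4 cannot be avoided by any later answer. It also catches the first-insulin patient who has not started, although Question 7 on its own would keep a not-yet-used answer.
- Two patients with the same history (rows 2 and 3) get opposite outcomes, depending on how they read a Question 7 that is worded for ongoing use.
- For a first-insulin patient, every option at Question 8 is untrue. The same holds for a patient who remembers an earlier insulin of another strength. The two 100 U/ml options are false, the residual option misstates the reason, and the last option is false and ends the survey.

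**2. Size of any effect on reported understanding**

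The documents give no figure for stopping, for reasons for stopping, or for understanding among patients who stopped. The inputs here are assumptions: share stopped s = 15%, understanding among continuing users c = 75%, among those who stopped d = 50%. Let f be the fraction of those who stopped that the screener ends.

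True value = (1 − s)c + s·d = 0.85 × 75% + 0.15 × 50% = 71.25%.

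Reported value = [(1 − s)c + s(1 − f)d] / (1 − s·f).

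- f = 1: 63.75/0.85 = 75.0%, difference 3.75 points.
- f = 1/3: (63.75 + 5.00)/0.95 = 72.4%, difference 1.1 points.
- f = 0: 71.25%, difference 0.

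At f = 1 the difference equals s(c − d) = 0.15 × 25 = 3.75 points. Its sign is the sign of c − d, which nothing in the Protocol fixes.

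For scale, the formula in Section 9.5 reproduces all five half-widths in Table 1 (5.9, 5.7, 5.4, 4.7 and 3.5%). At 75% it gives 1.96 × √(0.75 × 0.25/280) = 5.1%. The largest illustrative difference is 3.75/5.1, or about 0.7 of a half-width.

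**3. Question 8**

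If 10% of patients start the product with no earlier insulin (again an assumption), 0.10 × 280 = 28 respondents in a sample of 280 would have no true answer.

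**The case against.** Four arguments on the other side have weight.

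**Current users may have been meant.** Section 9.2.2 uses the present tense, and Section 9.9 speaks of patients being treated with the product. If so, removing those who stopped is intended. This stands as a possibility, but then Section 9.2.1 and Question 6 are the texts out of line and the contradiction remains. The gap in Question 8 is unaffected.

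**Not everyone who stopped is removed.** A reader might infer that the screener ends the survey for all patients who stopped. The printed logic does not support that: a patient on another insulin can give a past duration at Question 7 and continue. Only a 'No' at Question 4 is unavoidable.

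**Bias is not shown.** A reader might infer that understanding is biased upward because patients who stopped did so after a dosing problem. The Protocol gives no reasons for stopping, and such a patient could know the messages better. The direction is open.

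**Subgroups and never-users.** First-insulin patients who choose the don't-know answer leave both named 100 U/ml groups clean, and Section 9.7 confines these subgroups to what the questionnaire captures. What is lost is the ability to tell them from patients who cannot remember. Not-yet-users do reach the behaviour item "I think about the important safety information for Humalog 200 units/ml KwikPen to remind myself of the risks when injecting my insulin", but Question 7 identifies them and they can be separated in the analysis, so this is minor.

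Losses through Question 4 could also be counted, because Question 6 is still asked before the survey ends. Counting them does not recover their answers.

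**Conclusion.** The mismatch is established from the printed text and rests on no numerical assumption. The screener imposes current insulin use through Question 4, and leaves current product use to the respondent's reading at Question 7. Section 9.2.1, the Section 9.4 screening list and Question 6 require neither. Question 8 cannot be answered truthfully by a patient with no earlier insulin, or by one who remembers an earlier insulin of another strength.

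The effect on the main result is not established. Under the assumed 15%, 50% and 75%, the difference lies between 0 and about 3.75 points, and the upper end needs every patient who stopped to be ended, which the skip logic does not do. The effectiveness criterion in Sections 4.5 and 9.1 is a majority of respondents. Both 71.25% and 75.0% exceed it, so the illustration does not change the conclusion. The finding is worth acting on because the population is undefined as written, the prior-insulin data are compromised at collection, and the remedy is nearly free before fielding.

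**What to change.** 1. State in Sections 9.2.1 and 9.2.2 whether eligibility means ever prescribed or current use, and align Questions 4, 6 and 7 with that choice.
   - If ever prescribed: remove the termination at Question 4 when Question 6 is 'Yes', and add a non-terminating option to Question 7 for patients who used the product but have stopped.
   - If current use: change Section 9.2.1 and Question 6, and limit the conclusion to current users.
2. In either case, add two options to Question 8: no insulin before, and insulin of another strength.
3. As a minor point, report the behaviour item (Question 15C) without respondents who say at Question 7 that they have not used the product yet.

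The cost is a few response options, a change to the skip logic and matching text in the eligibility sections. Annex 1 still labels the patient survey a draft. No extra respondents are needed.
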